ILD	Interstitial Lung Disease
IV	Intravenous
IXRS	Interactive Web/Voice Response System
LD	longest diameters
LVEF	Left ventricular ejection fraction
MedDRA	Medical Dictionary for Regulatory Activities
MUGA	Multigated acquisition (scan)
NCI	National Cancer Institute
ORR	Objective response rate
OS	Overall survival
PFS	Progression-free survival
PK	Pharmacokinetic or pharmacokinetics
PR	Partial response
PROs	Patient reported outcomes
PWB	Physical well-being
QTc (QTcB; QTcF)	Heart rate-corrected QT interval (by Bazett's; by Fridericia's)
RECIST	Response Evaluation Criteria in Solid Tumors
SAE	Serious adverse event

ABBREVIATION	DEFINITION
SAP	Statistical analysis plan
SCCHN	Squamous cell carcinoma of the head and neck
SD	Stable disease
SWB	Social well-being
TEAE	Treatment-emergent adverse event
ULN	Upper limit of normal
WBC	White Blood Count

Approved

1. SCOPE

This Statistical Analysis Plan (SAP) is created based on Protocol U31287-A-U203 version 4.0, 13 JUN 2016. This version describes in detail the statistical methodology and the statistical analyses to be conducted for the above mentioned protocol. The analysis plan may change due to unforeseen circumstances. Any deviations to the planned statistical analyses specified within the SAP will be justified in writing and presented within the clinical study report.

Approved

2. STUDY OBJECTIVES

2.1. Primary Objectives

- To evaluate PFS in the HRG high expression population from subjects treated with patritumab + cetuximab + platinum-based therapy compared to placebo + cetuximab + platinum-based therapy

2.2. Secondary Objectives

- Evaluate OS
- Evaluate objective response rate (ORR)
- Refine the cutoff between HRG high and low expression based on clinical data from this study
- Assess the population PK of patritumab in subjects with SCCHN
- Assess the PK parameters of serum cetuximab and platinum concentrations when cetuximab and cisplatin or carboplatin (platinum-based therapy) are coadministered with patritumab in subgroup (n = 30) of subjects
- Evaluate the incidence of HAHA formation (anti-patritumab antibodies)
- Evaluate the safety and tolerability of the combination of patritumab + cetuximab + platinum-based therapy in first-line treatment of subjects with SCCHN

2.3. Exploratory Objectives

- Duration of response, time to response, time to disease progression, duration of SD from subjects treated with patritumab + cetuximab + platinum-based therapy compared to those treated on placebo + cetuximab + platinum-based therapy
- Explore potential exposure-response and possibly other biomarker relationships
- Evaluate disease specific patient reported outcomes (PROs) using the Functional Assessment of Cancer Therapy-Head and Neck (FACT-H&N) which assesses:
 - Physical well-being
 - Functional well-being
 - Social/Family well-being
 - Emotional well-being
 - Head and neck cancer symptoms

- Evaluate head and neck cancer symptoms using the FACT-Head and Neck Symptom Index (FHNSI), a 10-item instrument comprising items from the FACT-H&N
- Evaluate PROs using the EuroQoL-5 Dimensions-5 Levels (EQ-5D-5L) questionnaire, which assesses five dimensions:
 - Mobility
 - Self-care
 - Usual activities
 - Pain/discomfort
 - Anxiety/depression

Approved

3. STUDY DESIGN

[figure not shown]
3.1. General Study Design and Plan

This is a multicenter, randomized, placebo-controlled, double blind Phase 2 study to evaluate the PFS and safety in recurrent/metastatic first-line SCCHN in subjects treated with patritumab plus cetuximab plus platinum-based therapy compared with subjects randomized to the control arm consisting of placebo plus cetuximab plus platinum-based therapy.

Adult subjects with metastatic SCCHN originating from the oral cavity, oropharynx, hypopharynx, and larynx with documented disease recurrence following previous treatment for non-metastatic disease will be studied.

Approximately 105 subjects will be randomized 1:1 to the patritumab and the control arms stratified by HRG value (high versus low) and HPV status (positive vs negative). Approximately 70 HRG-high and approximately 35 HRG-low subjects will be randomized. When one HRG stratum is filled with the required sample size, the enrollment in that HRG stratum will cease. The initial cut-off for HRG high versus low before randomization was set using the median HRG delta Ct value (0.93) of commercial tissue samples and was increased based on further samples to 1.50 on 29JUL2016. See Figure 3.1.1 for a schematic of the study design.

Figure 3.1.1: Phase 2 Study Design

[figure not shown]
The enrolled subjects will be stratified by HRG (high, low) and HPV (positive, negative)

There will be two treatment arms:

1. Patritumab + cetuximab + platinum-based therapy with HRG high and HRG low subjects
2. Placebo + cetuximab + platinum-based therapy with HRG high and HRG low subjects

Figure 3.1.2 illustrates the order and timing of the treatments involved.

Figure 3.1.2: Order and Timing of Treatments

Patritumab initial loading dose is 18 mg/kg IV (or placebo) over 60 minutes followed in cycle 2 and beyond with a maintenance dose of 9 mg/kg IV over 60 minutes (\pm 10 minutes) every three weeks. Infusion time can be extended to a maximum of 120 minutes for subjects unable to tolerate the 60 minute infusion. Cetuximab initial dose at 400 mg/m² IV is given as a 2-hour infusion followed by 250 mg/m² over 60 minutes weekly.

One hour after the end of the cetuximab administration (on the weeks when cetuximab and platinum therapy are coadministered) infuse with either:

- Cisplatin at 100 mg/m² IV infused over 1 hour, every three weeks up to a maximum of 6 cycles. Pretreatment hydration with 2 liters of fluid prior to a cisplatin infusion is recommended and should adhere to institutional standards. Adequate hydration and urinary output must be maintained during the following 24 hours. Other pretreatments such as anti-emetic prophylaxis and posttreatments such as hydration are up to the discretion of the Investigator. This can be given in a separate infusion during patritumab and cetuximab infusion; or
- Carboplatin, IV bolus over 30-60 minutes, every 3 weeks for a maximum of 6 cycles. AUC 5 is the target. The carboplatin dose will be calculated using the Calvert formula: Carboplatin Dose (mg) = 5 x (glomerular filtration rate [GFR] + 25). Estimated serum creatinine clearance (mL/min) calculated using the modified Cockcroft-Gault equation also be used as an estimate for GFR. The carboplatin dose is required to be re-calculated for every dosing based on the current GFR (or creatinine clearance as an estimate of GFR as per the protocol).

Pre- and post-treatments are up to the discretion of the investigator.

For the purpose of collecting survival data, the duration of the study will be until all subjects have died or a minimum of 13 months after the last subject is randomized whichever comes first, approximately 22 months for PFS and 25 months for OS.

The screening period is up to 14 days. Each cycle of treatment will be 21 days. There is no limit to how many cycles for patritumab and cetuximab treatment. Treatment will continue without interruption in subjects with CR, partial response PR, or SD. However, platinum treatment (cisplatin or carboplatin) will be given up to a maximum of 6 cycles. Subject participation is expected to be approximately 20 months.

Subjects who demonstrate benefit from therapy may continue in the extension phase (Section 6.5) to receive treatment until progressive disease (PD), toxicity, withdrawal of consent, or starting another treatment for cancer therapy.

The study evaluation schedule is provided in Table 3.1.1 and Table 3.1.2

Approved

Table 3.1.1: Schedule of Events

Assessment	Tissue screen	Screen	Randomization	Cycle 1 (Weeks 1-3)						Cycles 2 & 3	Cycle 4 & all Subsequent Cycles	End of Cycle 6 & Every 4 Cycles	Every 6 weeks	End-of-Study Treatment Visit	40 Days After Last Dose ^a			
				Day 1			Day 2	Day 3	Day 8							Day 15	Day 1	Day 1
				Pre-dose	Dosing	EOI												
Visit Window (Days)		-14 unless otherwise indicated											21 days after last dose ^a					
Informed consent for tumor tissue	X																	
Informed consent (s) ^b		X																
Medical history (including smoking history) & demographics		X																
Inclusion / Exclusion		X																
Physical exam		X		X				X	X	X*	X*		X					
Vital signs		X		X		X		X	X	X*	X*		X					
Height & weight ^c		X		X ^d						X ^d	X ^d		X ^d					
ECOG		X		X			X	X	X	X	X		X					
Echo or MUGA ^e		X								X ^e	X ^e		X					
ECG (12-lead) ^e		X											X					
Con Meds		X		X	X		X	X	X*	X*			X					
Adverse Events	X ^f	X		X	X		X	X	X*	X*			X	X ^g				
PRO assessments ^h				X					X	X			X					
CBC differential & platelets ⁱ		X		X ^d			X ^d		X ^d									
Serum chemistries ⁱ		X		X ^d			X ^d		X ^d									
GFR or estimated serum creatinine clearance ^j		X		X					X	X								
Coagulation		X																
Urinalysis		X											X					
IxRS			X															
Intense PK ^k				X ^d	X	X	X	X	X	X ^f								
Sparse PK (all) ^l				X ^d	X					X			X					
HAHA sample ^l				X ^d						X			X					
Pregnancy test ^m		X											X					

Assessment	Tissue screen	Screen	Randomization	Cycle 1 (Weeks 1-3)						Cycles 2 & 3	Cycle 4 & all Subsequent Cycles	End of Cycle 6 & Every 4 Cycles	Every 6 weeks	End-of-Study Treatment Visit	40 Days After Last Dose ^a			
				Day 1			Day 2	Day 3	Day 8							Day 15	Day 1	Day 1
				Predose	Dosing	EOI												
Patritumab Adm ⁿ					X					X	X							
Cetuximab Adm ^o					X			X	X	X	X							
Platinum Adm ^p					X					X	X							
PGx sample ^q				X ^d														
Tumor assessments ^r		X										X ^s	X					
Survival follow-up														X ^t				
Additional biomarker blood samples ^u				X ^u						X ^u		X ^u	X ^u	X ^u				

- a Last dose of any study drug administered.
- b Informed consent for main study (mandatory) and pharmacogenomics (optional).
- c Height measured only at Screening.
- d These assessments can be performed within 3 days prior to visit.
- e Echocardiograms/MUGA scans will be performed at Screening, Cycle 3, every third subsequent cycle, and End-of-Study Visit. Additional echocardiograms/MUGA scans and electrocardiograms may be performed at the discretion of the investigator. The same test (echocardiogram or MUGA) must be used for a subject throughout the study.
- f Collect SAEs only related to the biopsy procedure.
- g At 40 days after the last dose of study drug, a telephone call will be placed to the subject to record adverse events.
- h PRO assessments will be administered before any study-related procedures are performed.
- i Results must be available prior to dosing.
- j At Screening, either GFR or the estimated serum creatinine clearance (mL/min) as an estimate of GFR will be calculated. The estimated serum creatinine clearance rate (CrCl; mL/min) will be calculated using the modified Cockcroft-Gault equation (Appendix 17.1). The estimated GFR will also be calculated before each cisplatin or carboplatin administration. This will be performed only until completion of chemotherapy.
- k Intensive serum PK in a subgroup of 30 subjects samples will be collected. See **Error! Reference source not found.** in the protocol for detailed information on sampling times.
- l See **Error! Reference source not found.** in the protocol for detailed information on sampling times.
- m Pregnancy test must be confirmed negative before dosing. Additional pregnancy testing may be done at the discretion of the Investigator and/or if required by local regulations for women of child-bearing potential.
- n Patritumab administered initially at 18 mg/kg and thereafter 9 mg/kg every 3 weeks as a continuous intravenous infusion over 60 minutes (±10 minutes). Infusion times can be extended to a maximum of 120 minutes for subjects unable to tolerate the 60-minute infusion.
- o Cetuximab infusions administered initially at 400 mg/m² IV over 2 hours and 250 mg/m² over 1 hour weekly. Cetuximab is administered 60 minutes after patritumab administration. Cetuximab is given on Days 1, 8, and 15.
- p Cisplatin infusions administered at 100 mg/m² IV over 1 hour and every 3 weeks up to a maximum of 6 cycles. For pre- and post-treatment hydration see **Section Error! Reference source not found.** in the protocol and according to institutional standards. Creatinine clearance required prior to cisplatin administration. Cisplatin administered 1 hour after cetuximab administration. If carboplatin is selected instead of cisplatin, administer carboplatin at AUC of 5 over 30-60 minutes every 3 weeks for a maximum of 6 cycles. See **Section Error! Reference source not found.** in the protocol for carboplatin.

- q Genetic sampling is optional.
- r Tumor measurements will be assessed per RECIST Version 1.1. Baseline scans to be performed as part of eligibility during Screening. Existing radiographic scans can be used for the baseline evaluation if the scans were performed within 4 weeks prior to randomization.
- s Tumor assessments are to be performed every 6 weeks to Week 24 (+/- 3 days), then every 12 weeks (+/- 7 days) thereafter.
- t After discontinuation from study treatment, follow-up information for survival will be obtained per telephone approximately every 3 months for a minimum of 13 months.
- u Additional biomarker samples:
Collect blood sample for cfDNA predose Cycle 1 Day 1, predose Cycle 2 Day 1, End of Cycle 6, predose every 4 Cycles, at progression (end of study treatment), and 40 days after last dose of study drug administered.
Collect blood samples for exosome at: predose Cycle 1 Day 1, predose Cycle 2 Day 1, and End of Cycle 6. Refer to the laboratory manual for instructions on collection and management of samples.
- * Can be collected on Days 8 and 15 in all subsequent cycles at the discretion of the Investigator.
- † Corresponds to Cycle 1, Day 21 (504 hrs)—see **Error! Reference source not found.** in the protocol.

Approved

Table 3.1.2: Schedule of Events for Extension Phase

	Additional cycles		Every 3 months	End of Treatment	40 days after last dose ^a
	Predose	Dosing			
Visit Window (Days)					
Physical Exam	X			X	
Vital Signs	X			X	
Adverse Events	X				X
CBC diff and platelets ^b	X ^b			X ^b	
Serum chemistries ^b	X ^b			X ^b	
HAHA and PK sample ^c			X		
Patritumab Adm ^d		X			
Cetuximab Adm ^e		X			
Additional biomarker blood samples			X	X	X

a Last dose of any study drug administered.

b CBC and chemistries must be performed within 3 days of dosing

c For subjects with positive HAHA at the End of Study Treatment visit, additional serum HAHA samples should be collected every 3 months up to 1 year from the last dose of study drug or if the subject starts another therapy for cancer, or withdraws consent from the study, whichever occurs first.

d Patritumab administered at 9 mg/kg every 3 weeks as continuous intravenous infusion over 60 minutes (± 10 minutes). Infusion times can be extended to a maximum of 120 minutes for subjects unable to tolerate the 60 minute infusion.

e Cetuximab is infused at 250 mg/m² over 1 hour weekly. Cetuximab can be administered directly after patritumab administration.

Approved

3.2. Study Population

Adult subjects with metastatic SCCHN originating from the oral cavity, oropharynx, hypopharynx, and larynx with documented disease recurrence following previous treatment for non-metastatic disease will be enrolled. A subject is considered enrolled in the study upon the Investigator or designee obtaining written informed consent from the subject, and upon determination that all inclusion and exclusion criteria have been satisfied.

3.3. Randomization and Blinding

3.3.1. Randomization

Approximately 105 subjects who have an HRG expression value and HPV status (+/-) will be assigned randomly in a blinded manner by the Interactive Web/Voice Response System (IXRS) to the patritumab or the control arms in a 2:1 stratification (approximately 70 HRG-high and approximately 35 HRG-low subjects)

The IXRS will manage the number of HRG-high and HRG-low patients randomized. Once the maximum number of HRG-low subjects has been randomized, the IXRS will not allow enrollment of additional HRG-low subjects. To ensure balance between treatment groups, subjects will additionally be stratified according to HPV status (positive, negative).

Randomization to treatment groups will be achieved using IXRS. The time between randomization and the initiation of treatment should be as short as possible and no more than 3 business days.

3.3.2. Blinding

This study is randomized, placebo-controlled, double blinded study. The treatment assignments will be blinded to the subjects, the investigators, site staff, and all persons involved in reviewing the clinical data, including CRO personnel in clinical and trial management and Sponsor personnel, with the exception of the Data Monitoring Committee, who will review the unblinded clinical data on an ongoing basis.

3.3.2.1. Unblinding at Primary Analysis

At the point of primary analysis, as defined in Section 7 of this SAP, the treatment assignment for all subjects randomized will only be unblinded to CRO and sponsor statisticians and programmers directly involved in performing the analyses after data are reconciled and cleaned and a snapshot of the clean database is created. To minimize potential bias, subjects and investigators will not be informed about individual treatment assignment until study closure. Any datasets containing potentially unblinded information (i.e., patritumab PK and HAHA) will have their access restricted. The study statistician will maintain a list of the individuals who have access to individual treatment assignments and/or data that potentially unblinds the study. This list will include the date and level of unblinding and rationale for unblinding.

3.3.2.2. Unblinding at Study Closure

For the purpose of database lock and generation of the clinical study report (CSR), the study will be considered closed when OS data will be considered mature. At study closure, all subjects will be unblinded for final analysis after the final database is locked. Any subject remaining on study treatment and appears to continue to benefit (ie, SD or better) from treatment may continue to receive study treatment.

3.3.2.3. Emergency Unblinding

In the case of a rare emergency where, in the opinion of the Investigator, discontinuation of study drug is not sufficient and study treatment must be unblinded to evaluate further course of medical treatment. The investigator is encouraged to contact the CRO medical monitor to discuss their rationale for unblinding. However, to prevent delays to the investigator or medical personnel responding to a potentially emergent situation, unblinding of the study treatment will not be dependent upon the investigator receiving approval from the CRO medical monitor. The method for determining a subject's treatment assignment once a subject is randomized in the study is through the IxRS. The investigator and one designated subinvestigator will have access to perform emergency unblinding in the IxRS. The treatment assignment of the selected subject randomized at their site will be revealed to the investigator performing the IxRS call upon completion of the emergency unblinding call. The investigator must contact CRO medical monitor by telephone with an explanation of the need for opening the treatment assignment code within 24 hours of opening the code. A detailed procedure is described in the protocol.

3.4. Study Assessments

The table in Section 3.1, above, presents the visit schedule and procedures of the study to be conducted at each visit.

4. SAMPLE SIZE DETERMINATION

The primary efficacy endpoint is PFS. The sample size for this study is based on the number of required PFS events in the HRG-high stratum. For PFS, a clinically meaningful improvement is defined as 79% increase from median PFS of 4.2 months in the control arm to median PFS of 7.5 months in the patritumab arm (that is a HR of 0.56). A total of 70 HRG-high subjects will be randomized to observe 53 PFS events in the HRG high stratum assuming a one-sided alpha of 0.10, 80% power, and a 1:1 randomization ratio between 2 arms, a 12-month enrollment and 10-month follow-up, and 10% dropouts.

Under 2:1 (HRG high vs. low) stratification, a total of approximately 105 subjects (70 HRG high subjects and 35 HRG low subjects) will be randomized in both strata to observe at least 75 PFS events. The sample size from both strata combined will provide approximately 81% power to detect a HR=0.56 in PFS assuming one-sided alpha of 0.05 and other same assumptions above if HRG high stratum does not show statistical significance in PFS.

The sample size computation is performed using the test based on Survival Superiority Trials: Two Sample Test – Logrank Test: Given Accrual Duration and Study Duration in the EAST software (version 5.3, Cytel Inc.).

Approved

5. STUDY VARIABLES

5.1. Efficacy Variables

Efficacy variables include PFS, OS, ORR (CR and PR), duration of response, time to response, time to disease progression, and duration of SD.

Tumor response assessments, including subjects who discontinued from treatment, will be performed every 6 weeks (± 3 days) for the first 24 weeks independent of treatment cycle until disease progression, death, start of new anticancer therapy, withdrawal of subject consent, lost to follow-up, or study closure, whichever occurs first. After 24 weeks, tumor assessments will be performed every 12 weeks (± 7 days).

5.1.1. Primary Efficacy Variable

The primary efficacy variable is PFS. PFS is defined as the time from the date of randomization to the earlier of the dates of the first objective documentation of radiographic disease progression (per RECIST v1.1 as assessed by investigator) or death due to any cause. Progressive Disease is defined as $\geq 20\%$ increase in the sum of diameters of target lesions; taking as reference the smallest sum on study (this includes the baseline sum if that is the smallest on study). In addition to the relative increase of 20%, the sum must also demonstrate an absolute increase of at least 5 mm. (Note: the appearance of one or more new lesions is also considered progression).

Subjects with a global deterioration of health status requiring discontinuation of treatment without objective evidence of disease progression at that time should be reported as “clinical progression.” Every effort should be made to document objective progression even after discontinuation of treatment. Symptomatic deterioration is not a descriptor of an objective response: it is a reason for stopping study therapy. The objective response status of such subjects is to be determined by evaluation of target and non-target disease. If a radiographic tumor assessment has not been performed within 4 weeks of the time of clinical progression, then another radiographic assessment should be performed without waiting for the next regularly scheduled scan.

For equivocal findings of progression (ie, very small and uncertain new lesions, cystic changes, or necrosis in existing lesions), treatment may continue until the next scheduled assessment. If at the next scheduled assessment, progression is confirmed, the date of progression should be the earlier date when progression was suspected.

The rules for censored cases are defined as follows:

1. Subjects who are alive with no objective documentation of radiographic disease progression by the data cut-off date for the PFS analyses will be censored at the date of the last post-baseline evaluable tumor assessment. The evaluable tumor assessment is defined as the overall response for tumor assessment being not “Inevaluable” recorded on the Case Report Form (CRF) page “overall tumor assessment”. If there is no post-baseline evaluable tumor assessment, the subject will be censored at the date of randomization.

2. Subjects who start other anti-cancer therapy including surgical or radiologic intervention given with curative intent prior to progression or death will be censored at the date of the last post-baseline evaluable tumor assessment prior to starting other anti-cancer therapy. If there is no post-baseline evaluable tumor assessment prior to starting other anti-cancer therapy, the subject will be censored at the date of randomization.
3. Subjects who progress or die after ≥ 2 consecutive missed tumor assessment visits will be censored at the date of the last evaluable tumor assessment prior to progression or death. In this study, progression or death after ≥ 2 consecutive missed tumor assessment visits is defined as progression or death that occurs more than 13 weeks (two tumor assessment visits plus 1 week visit window) since the last post-baseline evaluable tumor assessment. If there is no post-baseline evaluable tumor assessment prior to the tumor assessment of progressive disease or death and progression or death occurs more than 13 weeks since the date of randomization, the subject will be censored at the date of randomization;
4. Subjects without baseline tumor assessment will be censored at the date of randomization.

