#### **11.4.1. Primary Efficacy Analyses**

The primary efficacy endpoint for this study is PFS. Progression free survival is defined as the time from the date of randomization to the earlier of the dates of the first objective documentation of radiographic disease progression (as per RECIST Version 1.1- see [Appendix 17.3](#)) or death due to any cause. Subjects who are alive with no objective documentation of (radiographic) disease progression by the data cutoff date for PFS analysis will be censored at the date of their last evaluable tumor assessment. Detailed censoring rules for PFS analysis will be specified in the SAP.

The primary analysis is PFS comparison between the patritumab arm and the control arm in HRG-high stratum of the FAS. The testing hypotheses to compare PFS between the patritumab arm versus the control arm will be performed in two steps. In step 1, the null hypothesis that PFS is the same for both arms in the HRG high stratum of FAS is tested at the one-sided 0.10 significance level. If this test in step 1 does not reject the null hypothesis, then in step 2A, the null hypothesis that PFS is the same for both arms in the FAS will be tested at the one-sided 0.05 significance level. If the test in step 1 is rejected, then in step 2B, the two-sided 80% confidence interval (CI) for hazard ratio (HR) of PFS

in the HRG low stratum of the FAS will be estimated. The results from both steps (PFS comparison in HRG-high stratum, and PFS comparison in FAS or PFS estimate in HRG-low stratum) will be used to guide the decision on future Phase 3 designs.

The comparison of PFS between the patritumab arm and the control arm will be performed using a log-rank test stratified by the stratification factors in both the FAS and the HRG high stratum of FAS. The stratification factors include HPV (positive vs other) and HRG (high vs. low, only for the FAS) at randomization. Kaplan-Meier methods will be used to calculate median PFS and CIs and generate Kaplan-Meier curves for PFS. Estimates of HR between 2 arms along with their two-sided 80% and 95% CIs will be calculated using stratified Cox's proportional hazards regression model. The model will include the treatment group as a covariate and the stratification factors used at randomization as strata.

The above analysis for PFS will be performed in the per-protocol analysis set.

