5.1.3.1. Duration of Response

Duration of response is defined as the time from the date of the first documentation of objective response (CR or PR) to the date of the first documentation of progressive disease (disease progression as assessed based upon tumor measurements and recorded on the CRF page “overall tumor assessment”). If a subject is discontinued or is lost to follow-up with no documentation of progressive disease, duration of response is defined as the time from the date of the first documentation of objective response to the date of the last evaluable tumor assessment as a censored value. The rules for censored cases are defined as follows:

Subjects who progress after ≥ 2 consecutive missed tumor assessment visits will be censored at the date of the last evaluable tumor assessment prior to the tumor assessment of progressive disease. In this study, progression after ≥ 2 consecutive missed tumor assessment visits is defined as progression that occurs more than 13 weeks (two tumor assessment visits plus 1 week visit window) since the last post-baseline evaluable tumor assessment. Subjects who start other anti-cancer therapy prior to progression will be censored at the date of the last post-baseline evaluable tumor assessment prior to starting other anti-cancer therapy.

Duration of response will be measured for responding subjects (PR or CR) only.

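### The 13-week PFS censoring limit equals two missed scans only while scans are 6-weekly; after Week 24 it also censors events that follow one missed scan, or none

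*SAP*

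**What the plan says.** Protocol 11.4.1 leaves the detail to the SAP: "Detailed censoring rules for PFS analysis will be specified in the SAP". SAP 5.1.1, rule 3, gives the intent: "Subjects who progress or die after ≥ 2 consecutive missed tumor assessment visits will be censored at the date of the last evaluable" scan. It then makes the intent operational as "progression or death that occurs more than 13 weeks (two tumor assessment visits plus 1 week visit window) since the last" evaluable post-baseline scan, or since randomization if there is none. One fixed number serves the whole study.

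The scan schedule is not fixed. SAP 5.1 says assessments "will be performed every 6 weeks (± 3 days) for the first 24 weeks independent of treatment cycle", and then: "After 24 weeks, tumor assessments will be performed every 12 weeks", with a ±7-day window. The schedule of events in SAP 3.1 agrees ("Tumor assessments are to be performed every 6 weeks to Week 24 (+/- 3 days), then every 12 weeks (+/- 7 days) thereafter"), as does Protocol Section 7.

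The same 13-week limit, with the same explanation, is repeated for duration of response (SAP 5.1.3.1). Duration of stable disease takes over those rules (5.1.3.4), and time to progression uses rules similar to those for PFS (5.1.3.3).

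**The concern.** The rule has a criterion (two missed visits) and a number (13 weeks). They agree while scans are 6 weeks apart and disagree once scans are 12 weeks apart, when 13 weeks is one visit plus one week. A progression or death after a single missed scan is then treated as if two had been missed. Even a progression on an attended, in-window scan can be censored.

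This is the primary endpoint in the primary population, and the analysis is triggered by 53 events. The error acts only late on the curves, where more patritumab than control subjects remain if the drug works as planned. It also censors subjects at a clean scan just before an observed event, which can be informative. The planned PFS sensitivity analyses (SAP 8.2.1 and 8.2.4.1) add clinical progression and re-cut HRG. Neither varies rule 3, so they would not reveal the problem.

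**Working it through.** **1. The plan's figure.** Two visits plus one week at the 6-week interval is 2 × 6 + 1 = 13 weeks. The stated number reproduces for the schedule up to Week 24.

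**2. It works in the 6-weekly phase (±3 days at each end).** With one scan missed, the largest gap to the next attended scan is 12 + 6/7 = 12.86 weeks, and the event is kept. With two missed, the smallest gap is 18 − 6/7 = 17.14 weeks, and the event is censored. So 13 weeks separates one miss from two, as intended. The branch that counts from randomization also lies in this phase and is sound.

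**3. It fails once a 12-week interval is involved.** Gaps from the last attended scan to progression at the next attended scan:

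| Scans | Missed | Nominal gap (weeks) | Extreme in-window gap (weeks) | Result at 13 weeks |
|---|---|---|---|---|
| Week 18 to 36 | 1 | 18 | minimum 18 − 10/7 = 16.6 | always censored |
| Week 24 to 48 | 1 | 24 | minimum 24 − 10/7 = 22.6 | always censored |
| Week 36 to 60 | 1 | 24 | minimum 24 − 2 = 22 | always censored |
| Week 24 to 36 | 0 | 12 | maximum 12 + 10/7 = 13.43 | can be censored |
| Week 36 to 48 and later | 0 | 12 | maximum 12 + 14/7 = 14.0 | can be censored |

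If visit dates are uniform within their windows (an assumption), 5% of Week 24–36 intervals and 12.5% of later ones exceed 13 weeks with nothing missed. An attended scan read as inevaluable also leaves the clock running, because rule 1 in SAP 5.1.1 does not count it as evaluable.

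**4. What the rule's own formula gives.** Adding the next two intervals and one week:
- last evaluable scan at or before Week 12: 6 + 6 + 1 = 13 weeks;
- Week 18: 6 + 12 + 1 = 19 weeks;
- Week 24 or later: 12 + 12 + 1 = 25 weeks.

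**5. How much of the trial is exposed.** Inputs are the medians of 4.2 and 7.5 months, 12-month enrolment and 10-month follow-up (SAP 4), and 30.4 days per month (SAP 8.2.1). Week 24 is 168/30.4 = 5.53 months. Under exponential PFS, S = exp(−ln 2 × 5.53/median), which is 0.40 for control and 0.60 for patritumab. The share of events by the 22-month cut that fall after Week 24 is 1 − (1 − S)/P(event by the cut), or about 35% and 47%.

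**6. Events wrongly censored (zero or one visit missed), HRG-high.** Simulation with 35 subjects per arm, the medians and timing above, no dropout, uniform visit dates, and deaths making up 0% or 20% of events:

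| Scans missed | Events before rule 3 | Wrongly censored | Share |
|---|---|---|---|
| 0% | 56.6–57.0 | 1.8–2.2 | 3–4% |
| 5% | 56.3–56.8 | 3.3–4.0 | 6–7% |
| 10% | 56.0–56.5 | 4.6–5.4 | 8–10% |
| 20% | 55.2–55.9 | 6.2–7.2 | 11–13% |

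Adding 10% dropout, with 15% deaths, gives similar figures: 1.7 of 51 events lost with none missed; 45.5 kept against 50.0 under the two-missed-visits criterion at 10% missed; and 41 against 47 at 20%. With every visit exactly on its nominal date, the loss is zero with no missed scans and about 6% at 10% missed.

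**7. Power.** The Schoenfeld formula at HR 0.56 and one-sided 0.10 gives 79.6% for 53 events, matching the planned 80%. Reducing 53 in the proportions above gives about 78.5%, 77.5%, 77% and 75–76% at 0%, 5%, 10% and 20% missed.

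**The case against.** The strongest reply is that the go/no-go result hardly changes. Simulating the log-rank test under the written rule and under a schedule-based rule (2,500 trials per setting, dropout included) gives the following, written rule first:

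- **Type I error:** 0.102 and 0.103 with no scans missed, 0.104 and 0.106 at 10% missed, 0.103 and 0.102 at 20%.
- **Power:** 79.2% and 79.5%, 76.6% and 77.9%, and 77.7% and 78.4% at the same rates.
- **Hazard ratio at 10% missed:** 0.541 and 0.551.

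Under the null the wrongful loss is equal by arm (7.1% and 7.2%). It differs only under the alternative (7.2% of control and 10.0% of patritumab events at 10% missed). This is a proof-of-concept trial at one-sided 0.10.

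That stands as a limit on the consequence. Four further points also stand:

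- If the 53 events are counted after censoring, the cost is delay; if before, it is power. The SAP does not say which.
- The case with no missed visit needs window drift or an inevaluable scan.
- Missed-scan rates, death share and uniform visit dates are assumptions.
- Extra scans at clinical progression, at end of treatment or when clinically indicated would shorten some gaps, so the simulated losses may be too high.

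None of this reconciles the rule's number with its criterion. The gap arithmetic uses only intervals and windows stated in the documents.

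**Conclusion.** The concern holds. From the move to 12-weekly scans, rule 3 censors events that its own criterion would keep, and nothing elsewhere in the SAP corrects it. If one scan is missed, progression at the next scheduled scan is always censored once a 12-week interval is involved. With none missed, it is censored when in-window drift takes the gap past 13 weeks (at most 13.43 or 14.0 weeks).

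The size depends on adherence: roughly 3–4% of HRG-high events with no missed scans, 8–10% at 10% missed and 11–13% at 20%, given exponential PFS at the planning medians. The bias is small. The hazard ratio falls by about 0.01 in patritumab's favour, the patritumab median rises by about 0.3 months at 10% missed, and type I error is not inflated. There is little room to absorb lost events: 70 subjects yield about 59 events without dropout and about 53 if 10% contribute none.

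The rule should be corrected before unblinding. Otherwise the programmer must choose between the rule's words and its number on the primary endpoint, possibly after treatment is known.

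**What to change.** In SAP 5.1.1 rule 3 and in 5.1.3.1, replace the fixed 13 weeks with a limit tied to the schedule: censor at the last evaluable scan only if the event falls later than the planned date, plus one week, of the second scheduled assessment after that scan. Counted from the nominal visit date, this is 13 weeks for a last evaluable scan at or before Week 12, 19 weeks at Week 18 and 25 weeks at Week 24 or later. Using nominal dates absorbs the ±7-day drift.

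The general sentence should be the rule and the three figures only examples, because an unscheduled or end-of-treatment scan (at Week 15 or 21, say) has no nominal date of its own. For such a scan, take the next two scheduled visits. Counting missed scheduled visits directly would serve equally well.

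Sections 5.1.3.3 and 5.1.3.4 then inherit the correction. The SAP should also state whether the 53-event trigger is counted before or after censoring.

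The cost is one paragraph of SAP text and one change to the derivation before unblinding. No new data are needed.
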